7.2.3. Exploratory Analyses

The exploratory efficacy endpoints include:

1. Change from baseline in the need for blood transfusions
2. Change from baseline in disease-associated biomarkers such as estimated glomerular filtration rate (eGFR), spot urine albumin:creatinine ratio, and plasma brain natriuretic peptide (BNP)

3. Change from baseline in QoL, assessed via the Functional Assessment of Chronic Illness Therapy -Fatigue (FACIT-FATIGUE) and European Organisation for Research and Treatment of Cancer, Quality of Life Questionnaire-Core 30 Scale, Version 3.0 (EORTC QLC-C30) scales
4. Change from baseline in major adverse vascular events (MAVEs). The definition of a MAVE is provided in Section 13.8 of the protocol.

A summary of the number of pRBC transfusion requirements up to Day 253 (Day 281 for Cohort 4) will be presented including number of transfusion episodes and units transfused. For patients who had received transfusions in the year prior to receiving ALXN1210, the number (%) of patients achieving transfusion independence will be presented.

Descriptive statistics for the exploratory efficacy endpoints of absolute, changes and percentage changes from Baseline in disease associated biomarkers such as eGFR, spot urine albumin:creatinine ratio, and BNP will be produced for each visit, by cohort and overall. Baseline is defined as the last non-missing assessment value prior to the first ALXN1210 infusion. Additionally, patients' stages of chronic kidney disease (CKD) will be assigned based on the following classifications and the number (%) of patients in the different CKD stages will be presented over time. CKD stages are defined as: Stage 1 CKD, eGFR greater than 90 ml/min/1.73 m² and there is presence of proteinuria; Stage 2 CKD, eGFR 60-89 ml/min/1.73 m² and there is presence of proteinuria; Stage 3 CKD, eGFR 30-59 ml/min/1.73 m²; Stage 4 CKD, eGFR 15-29 ml/min/1.73 m²; Stage 5 CKD, eGFR less than 15 ml/min/1.73 m². Patients failing to meet the criteria for Stages 1 to 5 will be classified as not having CKD.

The scoring guideline for the FACIT-FATIGUE and EORTC QLQ-C30 instruments will be used to calculate a FACIT-FATIGUE score and the different EORTC QLQ-C30 scale scores. Refer to Section 9.5 for a more detailed description of the FACIT-FATIGUE score and EORTC QLQ-C30 and the scoring methods. Descriptive statistics of FACIT-FATIGUE scores and changes from baseline in FACIT-FATIGUE scores will be produced for all study visits at which they are collected, by cohort and overall. Changes from baseline will be analyzed in the same manner as described for the primary efficacy endpoint utilizing the MMRM approach and Wilcoxon signed-rank test.

The number of any treatment emergent MAVEs (n) and number of patients with events (n, %) will be displayed by cohort and overall. Each of the MAVE categories will be similarly summarized. Patients having multiple MAVEs within a category will be counted once in that category.

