## 16.6. Efficacy Analysis

Efficacy analyses will be performed on the FAS, which include the Safety Set subset with a baseline and at least 1 postbaseline LDH measurement.

Absolute LDH levels, and the change and percent change from baseline will be summarized at all study visits. Baseline is defined as the average of all available assessments on or prior to the first ALXN1210 infusion. A mixed model for repeated measures (MMRM) with the fixed, categorical effect of visit and fixed, continuous effect of baseline LDH levels as covariates will be fit to test whether changes and percent changes differ from zero at each time point. An unstructured covariance analysis will be used to model the within-patient errors. If this analysis fails to converge, the following structures will be tested and the final covariance structure will be determined by Akaike's information criterion: first-order autoregressive, compound symmetry, and Toeplitz method. The Kenward-Roger approximation will be used to estimate denominator degrees of freedom. As a sensitivity analysis, changes and percent changes from baseline will be analyzed, using the Wilcoxon signed-rank test. Graphical displays will be presented, as appropriate.

The percentage of patients with clinical symptoms will be summarized for all study visits.

Changes in hematologic measures will be similarly analyzed using an MMRM and Wilcoxon signed-rank test.

Scoring guidelines for the FACIT-Fatigue and EORTC scales will be used to calculate QoL scores. Changes from baseline in FACIT-Fatigue and EORTC scale scores will be summarized descriptively for all study visits, and analyzed using MMRM and Wilcoxon signed rank test.

Transfusion rates and the incidence rate of MAVEs will be summarized.

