4.1. Changes from Analyses Specified in the Protocol

There are no changes from analyses specified in the protocol apart from the inclusion of data up to the Day 281 visit for Cohort 4 (the first dose in the Extension Period) in the analyses.

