5.1.3. Exploratory Endpoints

The exploratory endpoints include:

- Change from baseline in the need for blood transfusions
- Change from baseline in the following disease-associated biomarkers: estimated glomerular filtration rate (eGFR), spot urine albumin:creatinine ratio, and plasma brain natriuretic peptide (BNP)
- Change from baseline in quality of life (QoL), assessed via the Functional Assessment of Chronic Illness Therapy (FACIT)-Fatigue Scale, version 4 and European Organisation for Research and Treatment of Cancer, Quality of Life Questionnaire-Core 30 Scale, Version 3.0 (EORTC QLQ-C30) scales
- Change from baseline in major adverse vascular events (MAVEs). The definition of a MAVE is provided in Section 13.5 of the protocol.

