7.1.3.2. Disease Characteristics and PNH Medical History

The following PNH disease characteristics will be summarized.

- Age (years) at PNH diagnosis.
- Method of PNH diagnosis.
- Years from PNH diagnosis to informed consent.
- PNH clone size (granulocyte, and red blood cell (RBC)) at screening.
- Peripheral red blood cell (pRBC) transfusion requirements in the year prior to receiving ALXN1210 including number of transfusion episodes and units transfused.
- First PNH symptoms.
- History of any major adverse vascular event (MAVE). The number of patients (n, %) with any history of MAVE and within a particular MAVE category (e.g. thrombophlebitis/deep vein thrombosis, pulmonary embolus, myocardial infraction, etc.) will be displayed.

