7.2.1.1. Handling of Dropouts or Missing Data

Missing data for primary, secondary and exploratory endpoints analyses will be handled as indicated for the specific analysis.

Missing data for QOL instruments will be handled as specified in the instructions for each instrument and as specified in Section 9.5 .

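### Transfusion counts cover a shorter window than the prior-year count with no rate per patient-year planned, and transfusion independence has no rule for patients who leave early

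*SAP*

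**What the plan says.** SAP 5.1.3 and 7.2.3 list the exploratory endpoint as "Change from baseline in the need for blood transfusions". Three pieces of planned analysis bear on it.

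- **On treatment (SAP 7.2.3):** "A summary of the number of pRBC transfusion requirements up to Day 253 (Day 281 for Cohort 4) will be presented", as episodes and units.
- **Before treatment (SAP 7.1.3.2):** the disease characteristics include "transfusion requirements in the year prior to receiving ALXN1210 including number of transfusion episodes and units transfused".
- **Independence (SAP 7.2.3):** "For patients who had received transfusions in the year prior to receiving ALXN1210, the number (%) of patients achieving transfusion independence will be presented". The term is not defined. The Day 253/281 window is implied by the preceding sentence but not restated.

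On missing data, SAP 7.2.1.1 says: "Missing data for primary, secondary and exploratory endpoints analyses will be handled as indicated for the specific analysis". Rules then follow for LDH (7.2.1), the hematologic parameters (7.2.2) and the quality-of-life scales (9.5). Section 7.2.3 gives none for transfusions.

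Protocol 16.6 says only: "Transfusion rates and the incidence rate of MAVEs will be summarized". It gives no time base for the rates.

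**The concern.** The endpoint is a change, yet for the counts the SAP specifies neither a change nor a rate per unit of time. It does specify changes for the hematologic parameters, the biomarkers and FACIT-Fatigue. The two counts cover different lengths of time: a full year before first dose, and about 36 weeks (40 in Cohort 4) after it. A reader who compares them sees a fall even if the drug does nothing, and every patient lost early deepens it.

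Independence raises a related problem. A patient who leaves untransfused after a few weeks has had little chance to need a transfusion, and nothing in the SAP stops that patient being counted as independent. The full analysis set (SAP 6.2) requires only a baseline and one post-dose LDH, and the first post-dose LDH is scheduled on Day 7 (Protocol Tables 4 to 7).

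There is no control arm, so before versus after is the only evidence the trial offers on transfusion need.

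**Working it through.** **Inputs.** Window ends are Day 253 and Day 281 (SAP 7.2.3), so elapsed time from Day 1 is 252 or 280 days. The comparison period is one year, 365 days (SAP 7.1.3.2). Cohort sizes are 6, 6, 6 and 6 to 8 (SAP 4, dosing schedule). Dropout is 15% (Protocol 16.3, SAP 9.3). The plan states no transfusion rate and no design figure for transfusions, so there is none to reproduce. An unchanged constant rate is assumed throughout, meaning no drug effect.

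**1. Window effect, full follow-up.** Apparent fall = 1 - T/365.

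- Cohorts 1-3: 1 - 252/365 = 31.0%.
- Cohort 4: 1 - 280/365 = 23.3%.
- Combined, 24 patients: mean follow-up (18 × 252 + 6 × 280)/24 = 259.0 days, a fall of 29.0%. With 26 patients: (18 × 252 + 8 × 280)/26 = 260.6 days, a fall of 28.6%.

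For example, 4 episodes in the prior year become 4 × 252/365 = 2.8 or 4 × 280/365 = 3.1. Cohort 4 also has 280/252 = 1.11 times the counting time of the other cohorts.

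**2. Adding dropout.** If 15% leave at times spread evenly over the window, with no later follow-up, mean follow-up is 0.85T + 0.15T/2 = 0.925T.

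- Cohorts 1-3: 233.1 days, a fall of 36.1%.
- Cohort 4: 259.0 days, a fall of 29.0%.
- Combined: 34.4% (24 patients) or 34.0% (26 patients).

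**3. Remaining untransfused by chance.** For a Poisson rate r per year, P(no transfusion by day t) = exp(-rt/365).

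| r per year | t = 84 days | t = 252 days |
|---|---|---|
| 1 | 79% | 50% |
| 2 | 63% | 25% |
| 4 | 40% | 6% |

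Short follow-up alone makes a patient look independent.

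**4. Effect of the missing withdrawal rule.** Suppose 15% of previously transfused patients leave, evenly over 252 days. The difference between counting untransfused leavers as independent and not doing so is 15 × (1 - exp(-x))/x points, with x = r × 252/365.

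| r per year | x | Swing (points) |
|---|---|---|
| 1 | 0.69 | 10.8 |
| 2 | 1.38 | 8.1 |
| 4 | 2.76 | 5.1 |
| 6 | 4.14 | 3.6 |

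The ceiling is 15, reached if every leaver is untransfused at exit. A drug that works lowers r and moves the swing towards that ceiling.

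Illustration of three possible rules, with assumed counts: 20 previously transfused patients, 3 leaving untransfused, and 10 of the 17 completers independent. Counting the leavers as independent gives 13/20 = 65%, excluding them 10/17 = 59%, and counting them as not independent 10/20 = 50%.

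**5. Within one cohort.** In a cohort of 6, one such patient moves the percentage by at least 1/6 = 17 points, because the denominator holds only previously transfused patients. In a Cohort 4 of 8 the corresponding minimum is 1/8 = 12.5 points.

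**6. Day 281 against Day 253 in Cohort 4.** The largest value over r of exp(-252r/365) - exp(-280r/365) is 3.9 points, at r = 1.37 per year. The longer window lowers Cohort 4's independence figure.

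**The case against.** The strongest reply is that the biased contrast is not in the plan. The prior-year count is in the baseline section and the on-treatment count in the efficacy section. No joint table, subtraction or percent reduction is specified, and both windows are labelled. This stands: the 31% and 23% measure what a reader would get by setting the two counts together. But these are the only planned count figures from which a change can be read, and the endpoint is a change.

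Second, it would be wrong to infer that no before/after measure is planned. Independence among patients transfused in the prior year is one. That also stands, which is why its undefined handling of early leavers matters.

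Third, a reader might infer that the SAP dropped the protocol's transfusion rates without declaring it, since SAP 4.1 states: "There are no changes from analyses specified in the protocol apart from the inclusion of data up to the Day 281 visit". The documents do not support this. The protocol never defines its rates, and the SAP implements the MAVE incidence rate from the same protocol sentence as "The number of any treatment emergent MAVEs (n) and number of patients with events (n, %) will be displayed by cohort and overall". The word may simply have been used loosely, so no departure is shown.

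Fourth, a reader might take the Day 281 window in Cohort 4 for an error. SAP 4 gives a reason for it (data at trough concentration), the effect on independence is small, and it runs against Cohort 4.

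Finally, the dropout figures are adverse-case. Protocol 8.3 asks patients who stop dosing to keep attending, so less follow-up may be lost than step 2 assumes. Excluding early leavers is also a defensible convention, and the fix reports it as a check.

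**Conclusion.** The point holds as a minor one. For the counts, the SAP gives no rate and no change, and a before/after reading is tilted towards the drug by 31% in Cohorts 1-3 and 23% in Cohort 4. Those two figures assume an unchanged constant rate and full follow-up. They need no assumption about how often patients are transfused.

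The missing rule for early leavers moves the combined independence percentage by about 4 to 11 points. This rests on 15% dropout among previously transfused patients, evenly timed exits, and unchanged Poisson rates of 6 down to 1 per year, none of which the documents give for transfusions. The absence of the rule is plain from the text; its size is illustrative.

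The endpoint is exploratory, p-values outside LDH are descriptive (SAP 7.2.1.4), and the primary LDH analysis and sample size are untouched.

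**What to change.** In SAP 7.2.3:

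1. Keep the counts. Beside them, report pRBC episodes and units per patient-year for the year before first infusion, and from first infusion to Day 253 (Day 281 for Cohort 4) or last contact. Use each patient's observed follow-up as the denominator, and show the paired change by cohort and overall.
2. State that patients who leave follow-up before the end of the window are not counted as transfusion-independent, and show the result with them excluded as a check. Keep Day 281 for Cohort 4; Day 253 may be shown as well.

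The cost is a few sentences and one or two table programs, with no new data. The prior-year figure is already annual. Follow-up from first infusion is study participation (SAP 7.3.1, counted from consent) minus the days from consent to first infusion. Time on treatment, also in 7.3.1, is the wrong base because it can end before follow-up does. Individual rates from very short follow-up will be erratic, so the group rate should be total events over total patient-time.

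The downside for the sponsor is a smaller apparent reduction in transfusions and possibly fewer patients counted as independent.

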### **13.4. Exploratory Markers of PNH**

Markers of PNH symptoms and comorbidities (ie, chronic kidney disease by urinary spot albumin:creatinine ratio and eGFR, and BNP for pulmonary hypertension) will be evaluated in the study as exploratory efficacy endpoints. Evaluation for changes in kidney function will be based on Investigator assessment and laboratory results of serum and urinary creatinine and eGFR. The estimated glomerular filtration rate will be calculated using the Modification of Diet in Renal Disease formula at the same time blood is drawn for chemistry assessments; specified in the Schedule of Assessments ([Section 7](#)). In addition, total serum LDH levels may be further analyzed as individual LDH isozymes (LDH1-5).

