#### **14.1.6.5. Urinalysis and Urine Chemistry**

Urine samples will be analyzed for the parameters listed in [Appendix A](#).

Urine samples will also be analyzed to measure proteins and creatinine in order to calculate the urine protein:creatinine ratio.

Urinalysis and urine chemistry assessments will be performed at the time points specified in the Schedule of Assessments ([Section 7](#)).

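### The CKD bands in SAP 7.2.3 leave gaps, and patients who fall in a gap, or read literally have no result, are counted as free of CKD

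*SAP*

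**What the plan says.** SAP 7.2.3 assigns each patient a CKD stage and tabulates the number (%) of patients by stage over time. The bands, in ml/min/1.73 m², are:

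- "Stage 1 CKD, eGFR greater than 90", with proteinuria
- "Stage 2 CKD, eGFR 60-89", with proteinuria
- "Stage 3 CKD, eGFR 30-59"
- "Stage 4 CKD, eGFR 15-29"
- Stage 5, below 15

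The residual rule is: "Patients failing to meet the criteria for Stages 1 to 5 will be classified as not having CKD".

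On precision, Protocol 13.4 says only: "The estimated glomerular filtration rate will be calculated using the Modification of Diet in Renal Disease formula". No rounding rule is given there or in SAP 7.2.3, and SAP 9.4 has no eGFR derivation.

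On missing data, SAP 7.2.1.1 says: "Missing data for primary, secondary and exploratory endpoints analyses will be handled as indicated for the specific analysis". The CKD paragraph of 7.2.3 then indicates nothing.

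On proteinuria, 7.2.3 names no test and no threshold. Protocol 13.4 collects a spot albumin:creatinine ratio. Protocol 14.1.6.5 adds: "Urine samples will also be analyzed to measure proteins and creatinine in order to calculate the urine protein:creatinine ratio". Appendix A also lists urine protein on the urinalysis panel.

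**The concern.** A residual category that takes in everyone not staged is safe only if the stages cover every possible value and every patient has data. Neither condition is met here. Stage 1 uses a strict inequality at 90 while Stage 2 stops at 89, so 90 belongs to neither. The ranges for Stages 2 to 4 end one unit below the next band, which leaves further gaps if eGFR is not a whole number. The residual rule also asks for no result at all before it declares a patient free of CKD.

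Every one of these defaults goes the same way, towards fewer patients with CKD. In a table meant to show kidney status over time on treatment, that is a one-sided error. It would affect the count of patients without CKD and therefore the apparent shift between stages.

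**Working it through.** The plan gives no figure to reproduce, so the check has three parts: apply the rules as written, size the gaps under stated assumptions, and bound the missing-data effect.

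**1. The rules applied as written**, over eGFR 0 to 150:

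| eGFR | With proteinuria | Without proteinuria |
|---|---|---|
| 14.9 | Stage 5 | Stage 5 |
| 15 | Stage 4 | Stage 4 |
| 29.5 | no CKD | no CKD |
| 30 | Stage 3 | Stage 3 |
| 59 | Stage 3 | Stage 3 |
| 59.5 | no CKD | no CKD |
| 89 | Stage 2 | no CKD |
| 89.5 | no CKD | no CKD |
| 90 | no CKD | no CKD |
| 90.1 | Stage 1 | no CKD |
| missing | no CKD | no CKD |

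- *Whole-number eGFR with proteinuria:* 90 is the only value that meets no stage.
- *Steps of 0.1 with proteinuria:* 28 values meet no stage, namely 29.1-29.9, 59.1-59.9 and 89.1-90.0.
- *Rounding to a whole number* closes the gaps at 29-30 and 59-60 but still loses 89.5 to below 90.5. *Truncation* loses 90.0 to below 91.
- There is no gap at 15.

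**2. Size of the gaps.** The documents give no eGFR distribution. I assumed normal distributions with mean/SD of 70/25, 90/25 and 100/30. The number of results is 24 patients (4 cohorts × 6) × 3 post-baseline visits (Days 85, 169 and 253, Protocol Tables 4 to 7) = 72. For a gap from a to b,

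P = Φ((b − mean)/SD) − Φ((a − mean)/SD).

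For example, at 70/25 the 29-30 gap is Φ(−1.60) − Φ(−1.64) = 0.0548 − 0.0505 = 0.0043, or 0.43%.

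| Gap | 70/25 | 90/25 | 100/30 |
|---|---|---|---|
| 29 to 30 | 0.43% | 0.09% | 0.08% |
| 59 to 60 | 1.46% | 0.76% | 0.53% |
| above 89, up to and including 90 | 1.18% | 1.60% | 1.25% |

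The last gap counts only for the share p of patients with proteinuria. The total is P(29-30) + P(59-60) + p × P(89-90), computed before rounding; the number of results is that total × 72:

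| Decimals kept | 70/25 | 90/25 | 100/30 |
|---|---|---|---|
| p = 0 | 1.89% (1.36) | 0.84% (0.61) | 0.62% (0.45) |
| p = 0.5 | 2.48% (1.79) | 1.64% (1.18) | 1.24% (0.90) |
| p = 1 | 3.07% (2.21) | 2.44% (1.76) | 1.87% (1.35) |

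With whole-number eGFR only the value 90 is lost. The chance of rounding to 90 is 1.16%, 1.60% and 1.26%. With p = 1 that is 0.83, 1.15 and 0.91 of 72 results; with p = 0 it is none.

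**3. Missing data.** SAP 9.3 allows for 15% dropout: 0.15 × 24 = 3.6 and 0.15 × 26 = 3.9 patients. If all of them lacked a Day 253 eGFR, stayed in the denominator and were classified literally, the no-CKD row would gain up to about 15 percentage points.

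**4. By cohort.** SAP section 7 presents categorical results by cohort. One misclassified patient moves a cohort percentage by 1/8 = 12.5 to 1/6 = about 17 points.

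**The case against.** The best reply is that only the gap at 90 is certain. The bands are written as whole-number ranges, which fits eGFR reported as an integer at least as well as eGFR with decimals, and integers remove the gaps at 29-30 and 59-60. A programmer could read the Stage 1 limit as everything above 89. Since stages are assigned from eGFR, leaving out patients with no eGFR is a natural reading. The 15% is a sample-size allowance, not a forecast of missing Day 253 results: Protocol 8.3 asks patients who stop dosing to keep attending. eGFR and spot urine are scheduled at the same visits, so eGFR without a urine result should be uncommon. eGFR is also summarised as a continuous variable, and by-patient laboratory listings would let a reader trace a default classification.

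Much of this stands as a limit on size. The decimal and missing-data points are conditional, and the 15-point figure is a worst case. Between 59 and 60 without proteinuria, whether the no-CKD label is wrong depends on where the Stage 3 boundary is placed, and this gap supplies most of the p = 0 total. None of it removes the defect. Reading the Stage 1 limit as everything above 89 goes against the text. No other section repairs the bands. The SAP does state missing-data rules elsewhere (last observation carried forward in 7.2.1 and 7.2.2, item rules in 9.5), but none for CKD stage. Two programmers could produce different tables from this text.

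**Conclusion.** The concern holds. As written, the rule reports a patient with proteinuria and an eGFR of exactly 90 as free of CKD, whatever the reporting precision. The gaps at 29-30, 59-60 and 89-90 hold if eGFR keeps decimals. The default for missing eGFR, and for eGFR of 60 or more with no proteinuria result, holds if the residual rule is read literally. The undefined proteinuria criterion alone would be missing detail, but it decides between Stage 1 or 2 and no CKD for nearly everyone at 60 or above, so it should be settled in the same edit.

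The expected effect is at most one or two results among 72 under the assumed distributions, plus a missing-data effect bounded by the dropout rate. The table is exploratory and descriptive, so no primary, secondary or safety conclusion is at risk. It is a minor correction, worth making because it is cheap.

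**What to change.** In SAP 7.2.3, define contiguous bands on unrounded eGFR that stay with the plan's own boundaries and place each gap explicitly:

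- Stage 1: ≥90 with proteinuria
- Stage 2: ≥60 to <90 with proteinuria
- Stage 3: ≥30 to <60
- Stage 4: ≥15 to <30
- Stage 5: <15

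This moves the value 90 into Stage 1 and puts values between 59 and 60 in Stage 3. Applied in steps of 0.1 to patients with proteinuria, these bands leave no value unstaged.

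Replace the residual rule: a patient counts as not having CKD only with a non-missing eGFR of 60 or more and a negative proteinuria result. Show a missing eGFR, or an eGFR of 60 or more without a proteinuria result, in a separate missing row. State which urine measure and threshold define proteinuria; the sponsor must choose among the measures already collected.

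The cost is a few lines of SAP text and derivation code and one extra row in one exploratory table. No new data are needed.
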